5.3.4. Exploratory endpoints

- Changes in CRP, IL-2, IL-4, IL-8, IL-10, IL-12 (p70), IL-13, TNF- α and IFN- γ from baseline to Day 14, Day 28 and Day 56.
- FSD201 plasma exposure will be performed by analyzing plasma samples.
- Change or reduction in patient weekly PI-NRS after 28 and 56 days of treatment.

5.3.5. Safety endpoints

- Incidence and severity of treatment-emergent adverse events (TEAEs) throughout the dosing period
- Incidence and severity of treatment-emergent changes in laboratory values at Day 56
- Change from baseline in vital signs at each in-patient visit.

6. Study Design

6.1. Description of Study Design

This study is a randomized, double-blind, parallel-group, placebo-controlled study to evaluate the efficacy and safety of FSD201 in adult subjects with musculoskeletal nociplastic pain associated with MCAS.

The study design consists of up to 17 days screening period, a 56-day treatment period, and a 7-day follow-up period. Each subject will participate in the trial for up to 80 days.

6.2. Patient Recruitment

Subjects will be recruited by physician databases.

All subjects will provide written informed consent for the study at the beginning of the Screening Visit, prior to performance of any of the study procedures and collection of study data.

The subject's eligibility for randomization will be determined at Visit 2 according to the inclusion and exclusion criteria set forth in [Section 10.1](#).

A unique identification number will be given to study subjects to keep their information anonymous. Subject numbers will be assigned in sequential order (i.e., the first subject's identification number will be 001, etc.). This number will be used in all CRFs.

Demographic Data and Medical History

The subject's demographic information and medical history will be recorded at the Screening Visit and documented on the appropriate CRF. This will include:

- Demographic information: sex, age, race and ethnicity
- Medical history for the past 10 years prior to screening and other relevant history will be collected, including other types of pain (e.g., arthritis); surgeries; diabetes; cancer; cardiovascular events; and gastrointestinal problems
- Data on MCAS will be captured separately, in detail, including date of onset, and attempted treatments

After providing written informed consent, potential study subjects will be screened for study eligibility during the maximum 17 days screening and baseline period. During this time, subjects will complete daily entries to collect daily pain and sleep disturbance scores, and document rescue medication use (acetaminophen or diphenhydramine). Entries will be collected by means of a Study electronic Application (App) developed for this trial. The app can be installed on the patient's own device (assisted by the study coordinator), or the patient will be provided with a device (phone or tablet) to record these entries daily.

The values recorded on the last seven days before the randomization/Visit 2 will be used to determine the baseline scores. Subjects who completed entries in the App on at least 5 out of 7 days before randomization /Visit 2 and have an average pain intensity between 4.0 and 9.0 that meets the study-specified threshold and who continue to meet all other study eligibility criteria will be enrolled in the study.

Patients who meet the eligibility criteria will be randomized on Visit 2 in a ratio of 2:1 to receive 600 mg FSD201 or a placebo orally twice daily for 56 days. Subjects will take their first dose of the investigational either FSD201 or placebo in the clinic. An assessment for allergy or hypersensitivity reaction will be conducted immediately after the first dose; signs and symptoms to be evaluated include flushing, skin rash, urticaria, fever, dyspnea, bronchospasm, edema, angioedema, hypotension, and anaphylaxis.

Subjects will continue completing daily App entries throughout the 56 day treatment period including their 11-point pain scale over the last 24 hours, their sleep disturbance score, their rescue medication and their Investigational Compliance.

Subjects will return to the site at Day 14, Day 28 and Day 56/ Early termination visit. A phone call will be made to each subject seven (7) days after the last intake of the investigational product.

Subjects will be monitored for adverse events (AEs) from the date of first dose until the last follow-up visit (AEs noted between signing of Informed Consent Form (ICF) and first dose should be recorded as Medical History). Any SAEs occurring within 7 days after the last investigational medicinal product (IMP) intake will be collected. Efficacy and safety will be assessed as outlined in the schedule of events ([Table 1](#)).

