	
 ● Percentage of subjects achieving $\geq 50\%$ reduction in NPRS at Day 56² ● Change from baseline to Day 56 in PROMIS General Life Satisfaction -SF 5a ● The total amount of rescue medication used 
Note: ²DSIS averages will be calculated as follows: Baseline: calculated weekly average from Day -7 to Day -1 Day 56: calculated weekly average from Day 49 to Day 55
 
Exploratory endpoints
 
 ● Changes in CRP, IL-2, IL-4, IL-8, IL-10, IL-12 (p70), IL-13, TNF-α and IFN-γ from baseline to Day 14, Day 28 and Day 56; ● Estimation of Plasma levels of PEA as measured at baseline, day 14, Day 28 and Day 56 ● Change or reduction in patient weekly PI-NRS after 28 and 56 days of treatment 
Safety endpoints
 
 ● Incidence and severity of treatment-emergent adverse events (TEAEs) throughout the dosing period; ● Incidence and severity of treatment-emergent changes in laboratory values at Day 56; ● Change from baseline in vital signs at each visit.
STUDY POPULATION:	Musculoskeletal Nociceptive Pain Associated with Idiopathic Mast Cell Activation Syndrome (Disorder) (MCAS/MCAD)
Number of Subjects:	60
Number of Groups:	2 (FSD201, placebo)
Age/sex:	≥ 18 and ≤ 75 , male and female
Selection of Patients	
Adults ≥ 18 years with chronic musculoskeletal nociceptive pain in three or more body regions secondary, more likely to Idiopathic MCAS are selected and randomized to receive either FSD201, 600 mg b.i.d. or placebo. 60 study subjects.
 
1. The subject is ≥ 18 and ≤ 75 years of age at the time of signing ICF;

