peak plasma concentration was seen to be about 250 ng/mL in about 2 hours as compared to 50 ng/mL in about 45 minutes in fasting state. However, it did not appear to affect the time to reach the peak of concentration of PEA in the high-fat diet, as shown in Figure 4. Peak plasma levels and total exposure during a dosing interval increased in a dose-proportional manner across the dose range 600 to 1200 mg following repeated oral doses. However, the $C_{min ss}$ appeared to increase less than in a dose-proportional manner, as shown in Figure 2.

There appears to be no significant accumulation of FSD201 following repeated doses with 600 and 1200 mg. Following multiple dosing, steady-state was achieved within seven days at the 600 mg dose level and within four days at the 1200 mg *b.i.d.* dose level, as shown in Figure 3.

SAD

[figure not shown]

Figure 2 Mean Plasma Pharmacokinetic Concentrations for FSD201 in the SAD Study (Part A)

MAD

[figure not shown]

Figure 3 Mean Plasma Pharmacokinetic Concentrations for FSD201 in the MAD Study (Part B, Day 1 through Day 7)

Fasted vs Fed

[figure not shown]

Figure 4 Arithmetic Mean Plasma Concentration vs Time Profiles of FSD-201 for single dose of 1200 mg in fed and fasted individuals

Overall, FSD201 following an oral administration of a single dose, ranging from 600 mg to 2400 mg, and multiple doses ranging from 600 mg to 1200 mg *b.i.d.*, were safe and well-tolerated in normal healthy subjects. No serious adverse events (SAEs) were reported for these studies. The safety results seen in this Phase I trial were consistent with published information. There were no Treatment-Emergent Adverse Events (TEAEs) related to clinical laboratory results, ECGs, and physical examination in both the SAD and MAD recipients. No clinically relevant differences were observed between the treatment groups with respect to mean values and changes from baseline for clinical laboratory results, vital signs, and ECG results.

In the SAD study, one vital sign abnormality (hypotension) was experienced by one subject in Cohort 2 [1200 mg], observed during the scheduled measurements, considered a TEAE. This TEAE was considered mild and represented a transient lowering of systolic blood pressure of less than 10 mmHg. Overall, no safety issues were observed for clinical laboratory, vital signs, ECGs, or physical examination results.

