6.4. Study Procedures and Evaluations

Visit Number	1		2	3	4	5	6	7	8	9	10	11	ET
Study Day	Day -17 to Day -8	Day -7 to Day -1	Day 0	Day 7	Day 14	Day 21	Day 28	Day 35	Day 42	Day 49	Day 56	Day 63	N/A
Type of Visit	On Site	N/A	On Site	Phone	On Site	Phone	On Site	Phone	Phone	Phone	On Site	Phone	On Site
Written informed consent	X												
Demographic data	X												
Medical and medication history	X		X										
MCAS/MCAD History	X												
Physical examination (1)	X		X		X		X				X		X
Body Mass Index (BMI)	X												
Weight and Vital signs [BP, pulse, RR] (2)	X		X		X		X				X		X
Safety Laboratory Testing (3)	X		X		X		X				X		X
HIV, Hepatitis testing	X												
Pregnancy test (4)	X		X		X		X				X		X
Urine drug screen	X		X		X		X				X		X
Blood test (biomarkers) (5)	X		X		X		X				X		X
FSD201 Plasma exposure			X		X		X				X		X
Review of Inclusion / Exclusion criteria	X		X		X		X				X		X
Sleep Disturbance SF (PROMIS)			X		X		X				X		X
Pain Interference (PROMIS)			X		X		X				X		X
General Life Satisfaction (PROMIS)			X		X		X				X		X
Fatigue (PROMIS)			X		X		X				X		X
Anxiety (PROMIS)			X		X		X				X		X
Pain Intensity Numerical Rating Scale (PI-NRS)	X		X		X		X				X		X
Pain Catastrophizing Scale (PCS)			X		X		X				X		X
Health Questionnaire (PHQ-9)	X												
Anxiety Disorder (GAD-7)	X												
Patient Global Impression of Change (PGIC)											X		X
Randomization			X										
Allergy Assessment			X										
Adverse event recording			X	X	X	X	X	X	X	X	X	X	X
Concomitant medication	X		X	X	X	X	X	X	X	X	X	X	X
Connect to patient App/provide device	X												
11-point NPRS	X	X	X	X	X	X	X	X	X	X	X		X
DSIS Sleep scale	X	X	X	X	X	X	X	X	X	X	X		X
Rescue medication intake recording	X	X	X	X	X	X	X	X	X	X	X		X
Review of patient results in App			X		X		X				X		X
Investigational product dispensing			X		X		X						
Investigational product return and accountability					X		X				X		X
(1) A detailed physical examination to be performed at Visit 1 and a focused exam to be performed at all other visits													
(2) Vital signs measurements [T, HR, BP, SO2, RR]													
(3) Safety Laboratory Testing (Hematology, Biochemistry, Urine analysis)													
(4) Serum pregnancy will be performed at Visit 1 screening; Urine pregnancy to be performed at all other visits													
(5) Biomarkers: At Visit 1, only Serum Tryptase performed; all biomarkers performed at other visits													
(6) To be performed within 14 (±2) days of discontinuation or withdrawal													

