Investigational product (FSD201 or placebo) will be dispensed at Visit 2 (one wallet containing 15 days treatment), Visit 4 (one wallet containing 15 days treatment), and Visit 6 (2 wallets for a total of 28 days treatment). Outside of the visits, subjects are to orally self-administer the investigational product *b.i.d.* at home during the Treatment Period. The last dose of investigational product is to be taken in the morning of Visit 10. The investigational product is to be taken with a glass of water, within 30 minutes of a meal/food.

Subjects who forget to take their dose at the usual required time should take it immediately upon noting that it was missed. If a dose is missed altogether, the subject should record this in the daily dose compliance tracker (App) and continue with the normal scheduled dose on the following dose.

Adherence to Treatment: Following App review the Investigator or Investigator's designee will determine adherence to treatment. Subjects will be asked to bring their medication at Visit 4 and Visit 6 for an investigational product count. Subjects who missed >20% of the doses will be considered non-compliant. Non-compliant subjects will be counselled to adhere to the medication regimen and will be used for a sub-analysis study.

Safety Measures

General Physical Examination: A general physical assessment of the major body systems will be performed at the Screening Visit (Visit 1). An abbreviated physical exam focusing on the previously identified abnormalities or any patient reported symptoms will be performed at Visit 2, Visit 4, Visit 6, Visit 10 and the Early Termination Visit(if applicable).

Pregnancy Test (if applicable): At the Screening Visit, a serum pregnancy test will be performed. At Visit 2, Visit 4, Visit 6, Visit 10, and Early Termination a urine pregnancy test will be conducted at the clinic.

Vital Signs: Sitting blood pressure, heart rate, body temperature, oxygen saturation using Pulse oximetry and breathing rate will be measured at each visit after the subject has been sitting quietly for at least 5 minutes. Data will be recorded in the appropriate CRF.

Clinical Laboratory (Non fasting): Clinical laboratory testing will be performed at the Screening Visit (to determine and confirm eligibility) Visit 2, Visit 4, Visit 6, Visit 10 (End of Treatment) and in the event of Early Termination as shown in Table 2. Blood (~15 mL) and urine samples will be collected. The clinical laboratory analyses will include:

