8.1.1. Investigational Therapy

All randomized subjects will receive the study drug from Day 0 to Day 56 (Visit 2 to Visit 10). Subjects will take one tablet in the morning and one tablet in the evening (i.e., approximately every 12 hours, approximately at the same time every day, and at least 8 hours apart) according to their randomized treatment arm assignment as described below:

Arm A: FSD201 600 mg tablet *b.i.d.* for oral administration after food.

Arm B: One placebo tablet (i.e., matching 600 mg FSD201 tablets) *b.i.d.* for oral administration after food.

The first dose of the study drug will be taken at the site.

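### The one dedicated hypersensitivity check comes immediately after the first oral dose, with no required on-site stay or Day 0 recheck: a modest first-dose safety gap

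*Combined protocol and SAP*

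**What the plan says.** Section 6.2 describes dosing at Visit 2 (Day 0) and then one dedicated check: "An assessment for allergy or hypersensitivity reaction will be conducted immediately after the first dose". The signs to look for include urticaria, angioedema, hypotension and anaphylaxis. Section 8.1.1 adds only that "The first dose of the study drug will be taken at the site". In Table 1 the row "Allergy Assessment" has a single mark, at Visit 2, with no footnote on timing or repetition.

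The tablet is oral. Section 7.1.3 gives the food condition: "The investigational product is to be taken with a glass of water, within 30 minutes of a meal/food". It also ties vital signs at each visit to five minutes of quiet sitting, not to time since dosing, and tells subjects at Visit 2 to telephone the site about adverse events that may need medical attention.

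Section 4.3 reports, for a single 1200 mg dose in healthy subjects with the fed figure first and the fasted figure second, that "peak plasma concentration was seen to be about 250 ng/mL in about 2 hours as compared to 50 ng/mL in about 45 minutes". The following sentence says of food that "it did not appear to affect the time to reach the peak of concentration of PEA in the high-fat diet".

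**The concern.** Dosing in the clinic with a named list of allergic signs shows that the sponsor regards a first-dose reaction as worth supervising. The stated timing works against that purpose. A check made at about time zero can see a reaction that appears at once. It cannot see one that depends on the tablet being absorbed, and nothing then keeps the subject on site or brings staff back for a second look.

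The population makes this worth raising. Section 4.1 describes MCAS as a condition that can involve anaphylaxis or episodes close to it. Section 8.2.2 prohibits mast cell stabilizers and inhibitors during the study. Section 10.3 excludes known hypersensitivity to PEA but does not name prior anaphylaxis. Phase I enrolled healthy subjects, and the protocol gives no tolerability data specific to MCAS.

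At stake is prompt recognition and treatment of an early reaction in a small number of supervised first doses. No endpoint estimate or error rate is involved.

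**Working it through.** The protocol gives no figure of its own to reproduce here, so the check sets the relevant places side by side.

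**Timing of the check against absorption**

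| Item | Source | Time after first dose |
|---|---|---|
| Hypersensitivity check | 6.2; Table 1 | immediate, taken as about 0 min |
| Stated fasted peak, 1200 mg | 4.3 | about 45 min |
| Stated fed peak, 1200 mg | 4.3 | about 2 h = 120 min |
| Next scheduled contact (phone) | Table 1 and its window | Day 7 ± 2 = Day 5 to 9 |
| Next site visit | Table 1 and its window | Day 14 (Day 12 to 15) |

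The check precedes the stated peak by about 45 − 0 = 45 minutes (fasted) to 120 − 0 = 120 minutes (fed). Section 4.3 is inconsistent on whether food delays the peak, but an immediate check comes first on either reading. No time to peak at 600 mg is given in the text. I assume that it lies in the 45 to 120 minute range.

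**Other Day 0 procedures that might close the gap**

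- *Adverse event recording.* Table 1 marks it at Visit 2. Sections 6.2 and 13 send events before the first dose to medical history, so recording at Visit 2 must be post-dose. It has no set time and may coincide with the immediate check.
- *Vital signs.* They are due at Visit 2 without a time relative to dosing. Having hypotension on the checklist implies a blood pressure reading at the immediate check, but no later one is required.
- *Plasma sample.* The synopsis lists "Estimation of Plasma levels of PEA as measured at baseline, day 14, Day 28 and Day 56", which suggests a pre-dose sample at Visit 2. Section 5.3.4 drops the word baseline, and section 12.2 records the time of last intake for samples that include Visit 2. The timing is unclear, so the sample neither secures a stay nor rules one out.
- *App entries.* The daily items in section 6.2 are pain, sleep, rescue medication and compliance, not reaction symptoms. Table 1 next schedules App review on site at Day 14.

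None of these requires the subject to be seen at a defined time after the first dose.

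**Extent and cost**

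- First doses: 60, split 2:1 as 40 FSD201 + 20 placebo.
- A 60-minute stay: 60 × 1 h = 60 subject-hours, or 60 / 3 = 20 hours per site if the three sites enrol equally.
- A 2-hour stay: 60 × 2 h = 120 subject-hours, or 120 / 3 = 40 hours per site.
- Extra blood pressure and pulse readings: 60 × 1 = 60.
- A 60-minute stay runs 60 − 45 = 15 minutes past the stated fasted peak and ends 120 − 60 = 60 minutes before the stated fed peak.

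**The case against.** The strongest reply is that the word immediately may mark the start of a period of watching rather than a glance at time zero. The checklist includes signs, such as fever and edema, that fit a period of observation. That is a fair reading. But no length is given, so three sites in two countries may each settle on a different one. The protocol refers to no site procedure that would fix it.

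The second reply is that the risk is low. Section 4.1 describes PEA as blocking histamine release and mast cell degranulation, and cites more than 3500 patients treated with few adverse events. The 600 mg dose is the lowest tested in Phase I, where single doses up to 2400 mg were judged safe with no serious adverse events. Section 10.3 also excludes chronic urticaria, raised tryptase and unstable disease. Stable histamine blockers and diphenhydramine are permitted. All of this stands and limits the point to a modest one. Permitted antihistamines may soften a reaction but do not detect it.

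The third reply is that time to peak is only a proxy for reaction onset. That also stands. The documents do not link reactions to plasma level, and the stated peaks are for twice the trial dose in healthy subjects.

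A reader might be tempted to go further in three ways.

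- One is to infer that the plan will miss some share of reactions, or that the adverse event results are biased. The documents give no reaction rate or onset time, and adverse events are collected in both arms from the first dose, so neither follows.
- Another is to treat the Phase I finding that "one vital sign abnormality (hypotension) was experienced by one subject in Cohort 2 [1200 mg], observed during the scheduled measurements" as a delayed reaction that an immediate check would miss. Section 4.3 calls it mild, with a fall below 10 mmHg. It does not describe it as hypersensitivity, and gives neither the time after dosing nor the arm. It adds little.
- The third is to take the Visit 2 plasma sample as certainly pre-dose. The sections conflict on that.

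**Conclusion.** The point holds as a modest safety gap. The plan's only dedicated hypersensitivity check is timed before meaningful absorption can be expected, and no stay or Day 0 recheck is required. Between that check and the Day 7 call, detection rests on the subject contacting the site.

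This rests on two assumptions: that some early reactions need absorption rather than appearing at once, and that the 45 to 120 minute range reported at 1200 mg is a reasonable guide for 600 mg with food. The food instruction is general, and the protocol does not separately state the fed condition for the in-clinic dose. The size of the gap cannot be expressed as a rate. No sample size, power or error figure is touched. It is worth changing because the remedy is cheap, not because a serious hazard has been shown.

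**What to change.** Keep the immediate check. Add the following to section 6.2 and as a footnote to the allergy row of Table 1:

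> Subjects will remain on site for at least 60 minutes after the first dose; the same signs and symptoms will be reassessed, with blood pressure and pulse, before discharge.

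Sixty minutes covers early absorption and the stated fasted peak, but not the stated fed peak of about 2 hours. The sponsor may extend the stay if it judges the fed peak relevant, which would double the time.

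The cost at 60 minutes is protocol wording, a longer Visit 2, about 60 subject-hours in total and 60 brief extra readings by existing staff. No extra visit or laboratory test is needed. Reactions that begin after discharge would still depend on self-report.

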6.3. Overall Program Design and Plan

A timeline of study activities is shown in [Figure 5](#).

[figure not shown]

Figure 5 Schematic of Clinical Activities from Visit 1 (Screening) until Visit 11 (Follow-up)

6.4. Study Procedures and Evaluations

Visit Number	1		2	3	4	5	6	7	8	9	10	11	ET
Study Day	Day -17 to Day -8	Day -7 to Day -1	Day 0	Day 7	Day 14	Day 21	Day 28	Day 35	Day 42	Day 49	Day 56	Day 63	N/A
Type of Visit	On Site	N/A	On Site	Phone	On Site	Phone	On Site	Phone	Phone	Phone	On Site	Phone	On Site
Written informed consent	X												
Demographic data	X												
Medical and medication history	X		X										
MCAS/MCAD History	X												
Physical examination (1)	X		X		X		X				X		X
Body Mass Index (BMI)	X												
Weight and Vital signs [BP, pulse, RR] (2)	X		X		X		X				X		X
Safety Laboratory Testing (3)	X		X		X		X				X		X
HIV, Hepatitis testing	X												
Pregnancy test (4)	X		X		X		X				X		X
Urine drug screen	X		X		X		X				X		X
Blood test (biomarkers) (5)	X		X		X		X				X		X
FSD201 Plasma exposure			X		X		X				X		X
Review of Inclusion / Exclusion criteria	X		X		X		X				X		X
Sleep Disturbance SF (PROMIS)			X		X		X				X		X
Pain Interference (PROMIS)			X		X		X				X		X
General Life Satisfaction (PROMIS)			X		X		X				X		X
Fatigue (PROMIS)			X		X		X				X		X
Anxiety (PROMIS)			X		X		X				X		X
Pain Intensity Numerical Rating Scale (PI-NRS)	X		X		X		X				X		X
Pain Catastrophizing Scale (PCS)			X		X		X				X		X
Health Questionnaire (PHQ-9)	X												
Anxiety Disorder (GAD-7)	X												
Patient Global Impression of Change (PGIC)											X		X
Randomization			X										
Allergy Assessment			X										
Adverse event recording			X	X	X	X	X	X	X	X	X	X	X
Concomitant medication	X		X	X	X	X	X	X	X	X	X	X	X
Connect to patient App/provide device	X												
11-point NPRS	X	X	X	X	X	X	X	X	X	X	X		X
DSIS Sleep scale	X	X	X	X	X	X	X	X	X	X	X		X
Rescue medication intake recording	X	X	X	X	X	X	X	X	X	X	X		X
Review of patient results in App			X		X		X				X		X
Investigational product dispensing			X		X		X						
Investigational product return and accountability					X		X				X		X
(1) A detailed physical examination to be performed at Visit 1 and a focused exam to be performed at all other visits													
(2) Vital signs measurements [T, HR, BP, SO2, RR]													
(3) Safety Laboratory Testing (Hematology, Biochemistry, Urine analysis)													
(4) Serum pregnancy will be performed at Visit 1 screening; Urine pregnancy to be performed at all other visits													
(5) Biomarkers: At Visit 1, only Serum Tryptase performed; all biomarkers performed at other visits													
(6) To be performed within 14 (±2) days of discontinuation or withdrawal													

Table 1 Schedule of Events

A schedule of events is shown in Table 1. Visits 3-11 may occur ± 2 days from the days listed in the table, except for Visit 4, which may occur from Day 12 to Day 15.

7. Description of Procedures

